## 5 Statistical analyses

#### 5.1 Baseline characteristics and comparability by arm

Descriptive statistics for school- and individual-level baseline characteristics will be shown by arm and will include the mean and standard deviation (SD) (or median and interquartile range if non-normal) for continuous variables and frequencies and percentages for categorical variables. The following characteristics will be described as in Tables A1-A4:

- School-level: number of participants, district, type of school (government vs. private), composition of students (proportion boarding), menstrual cup consent and assent rate, urban vs. rural location, and WASH facility quality (Table A1).
- Female students: district, age, schooling category (day vs. boarding), religion, ethnicity, type of primary caregiver, caregiver's education, household size, number of meals eaten the previous day, socioeconomic status score derived from a principal components analysis of household assets and materials variables, and baseline measures of primary and secondary outcomes (where available (Table A2 and A4)).
- **Male students:** district, age, schooling category (day vs. boarding), religion, ethnicity, type of primary caregiver, caregiver's education, household size, number of meals eaten the previous

day, socioeconomic status score, knowledge of puberty and menstruation, and myths and attitudes towards menstruation (Table A3 and A4).

Baseline imbalance by arm was explored prior to finalisation of the SAP and no substantial baseline imbalances were identified in the baseline population. No formal statistical testing was performed to examine differences in baseline characteristics between the trial arms, as any difference would have been due to chance if the randomisation was correctly performed.

### 5.2 Analysis of continuous outcomes

The intervention effect for each primary outcome (educational attainment and SDQ) and continuous secondary outcomes will be presented as the adjusted mean difference in the endline scores between arms with corresponding 95% confidence intervals (CI). The effects will be estimated using linear random-effects (RE) models using a random intercept for school to adjust for within-school clustering. The model will be adjusted for the cluster-level mean of the baseline outcome measure and stratification variables (district and high/low school-level UNEB score). Likelihood ratio tests (LRT) will be used to obtain p-values. The results will be presented as shown in Table A5.

### 5.3 Analysis of count outcomes

For count outcomes (i.e., number of knowledge questions correct among female and male participants), the intervention effects will be presented as incident rate ratios (IRR) with 95%CI estimated using RE Poisson regression models with a random intercept for school to adjust for within-school clustering. The models will include the cluster-level mean baseline outcome measure and stratification variables. The LRT will be used to obtain p-values. If there is evidence of over-dispersion, the RE negative binomial model will be used. If there are issues of non-convergence, the GEE Poisson or negative binomial model will be used. The results will be presented as shown in Table A5.

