#### Table 2. Secondary outcomes

Secondary outcome	Measures	Variable type	Data source	Eligibility
1. Knowledge of puberty and menstruation; myths & attitudes towards menstruation	
 
1a) Number of knowledge items answered correctly (out of 9).
 
1b) Number of myths & attitudes items with positive responses (out of 3)
 
	Count	Endline survey	All female and male participants (stratified by gender)
2. Menstrual practices at last menstrual period (LMP)	
 
2a) Use of only adequate menstrual materials that are appropriately cleaned or disposed of at LMP
 
2b) Mean score on Menstrual Practice Needs Scale (MPNS)[10]
 
	Binary Continuous	Endline survey	Female participants who reported having menstruated in the past 6 months 
3. Pain management at LMP	Use of an effective pain management method (at least 1 effective method and none of the ineffective methods listed  )	Binary	Endline survey	Female participants who reported having menstruated in the past 6 months, and who report pain at LMP 
4. Self-efficacy of MH	Mean score on Self-efficacy in Addressing Menstrual Needs Scale (SAMNS)[11]	Continuous	Endline survey	Female participants who reported having menstruated in the past 6 months 
5. Quality of life 	CHU9D score, calculated as a weighted sum using adolescent Ugandan utility tariffs	Continuous	Endline survey	All female participants
6. Prevalence of urinary tract infection (UTI)	Symptomatic UTI, defined as at least one genital symptom plus leucocyte esterase and/or nitrates with a urine dipstick test	Binary	Endline survey and urine Multistix 8 dipstick result	Female participants who reported having menstruated in the past 6 months 
7. School and class absence during menses	
 
7a) Odds of missing a full school day on period-days relative to non-period days
 
7b) Odds of missing lesson on a school day on period-days relative to non-period days
 
	Binary (per day) Binary (per day)	Daily diary	Random subsample of ~1500 post- menarchal female Participants 

8. School and class attendance overall	
 
8a) Odds of missing a full school day
 
8b) Odds of missing lessons on a school day
 
	Binary (per day) Binary (per day)	Daily diary	Random subsample of ~1500 post- menarche female participants 

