### Table A5. Intervention effect for continuous and count outcomes

	Control arm		Inte	rvention arm	Intervention effect	
	N	Mean (SD)	N	Mean (SD)	Adjusted mean difference (95% Cl) 	p- value
Primary outcomes (females)						
Education attainment						
SDQ score						
Secondary outcomes (females)						
Knowledge questions answered correctly 						
Myths and attitudes questions answered positively 						
MPNS score						
SAMNS score						
Confidence in Maths score						
Confidence in Science score						
Secondary outcomes (males)						
Knowledge questions answered correctly 						
Attitudes questions answered positively 						

Adjusted for baseline outcome measure, district, high/low school-level UNEB score, and school clustering Out of 9 questions Out of 3 questions

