### 9.2 Annex 2: Further details on the secondary outcome measures

#### Summary of changes made to secondary outcome measures and rationale

Changes to the measures of the outcomes from what was specified in the protocol paper and protocol v6.0 are as follows (*All measures not listed were unchanged*):

Outcome	Measure (protocol v4.0)	Revised measure	Rationale
(protocol v4.0)		(protocol v6.0)	
1. Knowledge of puberty and	Proportion answering all knowledge questions correctly.	Number of knowledge items answered correctly (out of 9)	To make full use of the count data and avoid a cut-off
menstruation;	Proportion answering all questions on myths correctly	Removed and combined with below	Not measured as separate construct
attitudes towards menstruation	Proportion with "good responses" on attitudes	Number of myths and attitude items with positive responses (out of 3)	To make full use of the count data and avoid a cut-off
	Proportion using manufactured methods only at LMP	Removed	Use of adequate materials incorporated into below measure
2. Menstrual practices at last	Proportion correctly washing and drying re-usable pads and/or menstrual cups at LMP	Removed	Denominator likely to be influenced by the intervention
period (LMP)	Proportion with 'adequate MHM at school' at LMP (Self- reported use of clean materials to absorb/collect blood, changed privately, safely, hygienically, and as often as needed)	Proportion using only adequate menstrual materials that are appropriately cleaned or disposed of at their last menstrual period	Restricted to use and disposal of clean materials to limit overlap with MPNS outcome
3. Knowledge and practices of pain	Proportion knowing 4 or more effective pain management methods (Use of painkiller, drinking water, using water bottle, exercise, relaxing, foods with lots of water)	Removed	Reduced number of measures to focus on practice of pain management which implies knowledge
management during LMP	Proportion who used an effective pain management method	Proportion who used an effective pain management method (at least 1 effective method and no ineffective methods)	Clarified that no ineffective methods could be reported
5. Quality of life and happiness	Mean CHU9D score	CHU9D score calculated as a weighted sum using adolescent utility tariffs	Clarified that score would be calculated using validated weights in our population

Solf	Self-reported measure of happiness		Reduced number of
		Removed	measures; moved to
пар			exploratory outcome

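### Poisson model for bounded item totals has no provision for under-dispersion, so inference on the 3-item myths and attitudes score can be too conservative, chiefly in boys; Section 5.3 and Table A5 also name different effect measures

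*SAP*

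**What the plan says.** Table 2 of the SAP gives secondary outcome 1 two measures, for girls and boys separately: 1a, the number of knowledge items correct out of 9, and 1b, the number of myths and attitudes items answered positively out of 3. Both are typed as counts.

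Section 5.3 presents count outcomes as "incident rate ratios (IRR) with 95%CI estimated using RE Poisson regression models with a random intercept for school", with p-values from likelihood ratio tests. Its bracketed description of the count outcomes mentions only the knowledge score, so 1b comes under the section only through its label in Table 2. Two departures are foreseen: "If there is evidence of over-dispersion, the RE negative binomial model will be used", and "If there are issues of non-convergence, the GEE Poisson or negative binomial model will be used". Neither concerns variance below the mean.

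The section ends: "The results will be presented as shown in Table A5". That table covers continuous and count outcomes together and lists both scores for each sex. Its single effect column is headed "Adjusted mean difference", with no rate-ratio column and no footnote for the count rows.

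**The concern.** A Poisson count has no upper limit and its variance equals its mean. A sum of three yes/no items has a ceiling, and its variance is usually below its mean. The negative binomial only adds variance, so the planned fallback cannot repair a misfit in the other direction. A school variance estimated at zero need not count as non-convergence, so the GEE fallback may not be triggered either.

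Where this happens, the model reports a standard error that is too large, and a real improvement in attitudes may be missed. Boys are most exposed, because with few participants per school the overstated within-school variance dominates.

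The second issue is one of wording. A ratio of mean scores and a difference in items are different effect measures, and the plan names one in the text and the other in the table.

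**Working it through.** **The plan's own figures.** Section 2.3 gives 60 schools (30 per arm), ICC 0.05 and a standardised difference of 0.2. The design effect is DE = 1 + (m − 1) × ICC. At m = 60, DE = 3.95 and the effective n per arm is 30 × 60 / 3.95 = 456; power is 84.3% (t, 58 df) against 84% stated. At m = 40, DE = 2.95 and power is 80.1% against 80% stated. Both reproduce. They concern continuous outcomes; the SAP states no precision for the count outcomes. For boys, Section 3.3 gives m = 15, so DE = 1 + 14 × 0.05 = 1.70.

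**Variance against mean.** For K items with proportion positive p and inter-item correlation r:
- mean = Kp
- variance = Kp(1 − p)(1 + (K − 1)r)
- variance/mean = (1 − p)(1 + (K − 1)r)

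With independent items this is 1 − p: 0.5, 0.3 and 0.1 at 50%, 70% and 90% positive. In addition, any score on 0 to 3 has variance of at most mean × (3 − mean), which is below the mean once the mean exceeds 2, whatever the correlation. Nine items differ: at p = 0.5 and r = 0.2 the ratio is 0.5 × 2.6 = 1.3, which is over-dispersion.

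**Effect on the standard error.** The true variance of a school mean is about V = variance × DE/m. The random-effects Poisson model cannot fit less than mean/m, because the school variance stops at zero. So

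model SE / true SE ≈ √(max(V, mean/m)/V),

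which, when above 1, equals 1/√[(1 − p)(1 + (K − 1)r) × DE].

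Boys, 3 items, 70% positive, independent items: V = 0.63 × 1.70/15 = 0.0714; mean/m = 2.1/15 = 0.14; √(0.14/0.0714) = 1.40.

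The approximation was checked by fitting the random-intercept Poisson model to simulated item totals: 60 schools, no effect, 400 runs per setting, Wald tests, no covariates.

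| Score, group | p | ICC | Approx. ratio | Simulated ratio | Type 1 error, Poisson | Type 1 error, school-means t-test |
|---|---|---|---|---|---|---|
| 3 items, boys, m = 15 | 0.7 | 0.05 | 1.40 | 1.39 | 1.5% | 6.2% |
| 3 items, boys, m = 15 | 0.9 | 0.05 | 2.43 | 2.38 | 0.0% | 5.5% |
| 3 items, girls, m = 60 | 0.7 | 0.05 | 1.00 | 1.02 | 5.8% | 6.2% |
| 3 items, girls, m = 60 | 0.9 | 0.05 | 1.59 | 1.58 | 0.2% | 5.0% |
| 3 items, girls, m = 60 | 0.7 | 0.01 | 1.45 | 1.50 | 0.2% | 3.5% |
| 9 items, boys, m = 15 | 0.5 | 0.05 | 1.08 | 1.11 | 2.5% | 4.0% |
| 9 items, boys, m = 15 | 0.5 | 0.01 | 1.32 | 1.25 | 0.8% | 5.5% |
| 9 items, girls, m = 60 | 0.5 | 0.05 | 1.00 | 0.96 | 7.0% | 5.5% |

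**Where it starts.** With independent items the ratio exceeds 1 once p > 1 − 1/DE. At ICC 0.05 that is 1 − 1/1.70 = 0.41 for 15 boys, 1 − 1/2.95 = 0.66 for 40 girls and 1 − 1/3.95 = 0.75 for 60 girls.

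**Sensitivity to item correlation.** With r = 0.2, the boys' 3-item ratio falls to 1/√(0.3 × 1.4 × 1.70) = 1.18 at 70% and 1/√(0.1 × 1.4 × 1.70) = 2.05 at 90%. For nine items in boys at 70% correct, the approximate ratio is 1.40 with independent items and 1.00 with r = 0.2.

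**A second simulation** used correlated probit items at 60–75% positive. It gave ratios of 1.13–1.77 for 3 items at 12 per school, 0.94–1.53 for 3 items at 40 per school, and 0.93–1.13 for 9 items. Its 3-item score ICCs were about 0.012–0.040, all below the SAP's 0.05, so its upper ends describe low-ICC settings.

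**Power.** An effect with 80% power under the true SE lies 2.80 SEs from zero. If the SE is inflated 1.39 times, the threshold is 1.96 × 1.39 = 2.72 and power is Φ(0.08), about 53%. At 1.18 times, the threshold is 2.31 and power is Φ(0.49), about 69%.

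**The case against.** A reader might infer that the plan always gives too-wide intervals for the 3-item score. The figures do not support that. For girls at the SAP's own ICC and 60 per school, with about 70% positive, the ratio is 1.02 and type 1 error 5.8%. The over-width needs few participants per school, a high proportion positive or a low residual ICC. Adjusting for the baseline cluster mean would tend to lower the residual ICC, but the SAP does not say by how much.

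Nor is the over-dispersion provision simply misdirected: correlated knowledge items can produce over-dispersion.

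It is also tempting to argue that a rate ratio is unsuitable because it is capped: a control mean of 2.4 out of 3 cannot give more than 3/2.4 = 1.25. A mean difference is capped at 0.6 for the same reason, so this does not favour one measure over the other.

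Section 5.7 plans GEE with robust standard errors and cluster-level analyses, neither of which relies on the Poisson variance. This is real but partial mitigation. They are sensitivity analyses for the primary and selected secondary outcomes, and the selection is not given. The bootstrap in Section 6.3 is only to be considered, and only for non-normality.

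On the effect measure, Section 5.3 does say rate ratio, and Table A5 may just be a shared shell lacking a label. That makes the mismatch easy to cure, but the table lists the count outcomes explicitly and offers them only a mean difference.

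**Conclusion.** The point holds in limited form. Section 5.3 has no provision for under-dispersion, and the 3-item score is under-dispersed at any mean above 2 and, with independent items, at any mean.

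The consequence is mainly for boys. At ICC 0.05 and 15 per school, the standard error is about 1.4 times too large at 70% positive and 2.4 times at 90% with independent items, or about 1.2 and 2.05 times with inter-item correlation 0.2. Girls are affected only with a high proportion positive or a low residual ICC. The 9-item score is little affected in the simulated settings (ratio 0.93–1.25), though nearly independent items with a high proportion correct would behave like the 3-item score.

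The proportions positive, the item correlations and the use of ICC 0.05 for these scores are assumptions, because the SAP gives no score distribution. The outcomes are secondary, and the error is mainly lost power rather than false positives. The mismatch between Section 5.3 and Table A5 rests on the text alone and needs no assumption.

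**What to change.** 1. Name the myths and attitudes score in Section 5.3 alongside knowledge.
2. For that score, and for knowledge for consistency, replace model-based Poisson inference with a method that does not force variance to equal the mean. Any of these would do:
   - the linear mixed model of Section 5.2, which fits Table A5 as it stands;
   - a random-effects binomial model with denominators 3 and 9, allowing for correlation between a student's items;
   - Poisson regression with standard errors robust to clustering by school, which keeps the rate ratio.
3. State the same effect measure in Section 5.3 and Table A5.

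The linear model needs the fewest edits but is not the only sound choice. The cost is SAP wording. A mean difference or odds ratio replaces the rate ratio, and an odds ratio would need its own label in Table A5; if the rate ratio is kept, Table A5 needs a column for it.

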## 2 Study Design

### 2.1 Trial design

The study was a parallel-arm, cluster-randomised controlled trial with a mixed-methods process evaluation, and economic and policy analyses. Schools (clusters) were randomised 1:1 to immediate delivery of the MENISCUS intervention or optimised usual care (provision of government menstrual management readers and circular). Schools randomised to the optimised usual care arm were offered the intervention after the endline assessment (approximately 1 year after randomisation). In this SAP, the term "intervention" refers to immediate intervention, and "control" to optimised usual care (delayed intervention, delivered after endline).

Female students who joined the S2-S3 class cohort during the intervention delivery period were eligible to be recruited. This "open cohort" design accommodates the dynamic school population, as students may both join and leave the class cohort during the intervention period. In the pilot study, 82% of participants present at baseline were present at the endline survey 9 months later [6]. Primary and secondary outcomes for female students will be assessed among participants present at endline, adjusting for cluster-level mean baseline measures of the relevant outcome where available. Knowledge and attitudes among male students will be assessed through a closed cohort. Further details are described in section 3.4 below.

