#### Male students

Fifteen male S2 students per school were randomly selected to be recruited into a closed cohort at baseline. The enrolment lists provided by the schools were used as the sampling frame. Students were replaced by the next student on the randomly ordered list if they were found to have left the school, had been absent for the previous 3 school weeks, did not consent, or were unable to be reached on 3 visits to the school. For schools where the total number of boys in S2 was less than 15, all boys were eligible for participation. A waiver was obtained for parent/guardian consent. Male participants were asked for written informed consent. All male participants with baseline data were included in the cohort, even if enrolled after intervention activities started in the District as it is a closed cohort.

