#### 3.5 Analysis populations

Primary analysis population: The primary analysis will be conducted according to intention-to-treat (ITT) principles. Schools will be analysed according to the arm they were randomised to regardless of whether they received the intervention. Enrolled female participants with endline survey or UNEB data will form the primary analysis population. Students who switched schools between baseline and endline will be analysed according to the school they are attending at endline.

Female closed cohort: An additional analysis will be carried out within the closed cohort of female participants recruited at baseline who are enrolled at the same school at endline. This replaces a classic per-protocol analysis (which is problematic as there is no clearly-defined appropriate comparison group of those who would have received the intervention if offered, in the control arm). The closed cohort analysis assesses the intervention effect among those who had the chance to be exposed to the intervention for the whole study period in both arms.

Male closed cohort: Outcomes among male students will be assessed in the closed cohort of male participants recruited at baseline who are enrolled at the same school at endline.

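### The male models adjust only for the school-mean baseline and leave each boy's own baseline score unused; the loss of precision is small, but the remedy is almost free

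*SAP*

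**What the plan says.** Section 5.3 covers both sexes: "For count outcomes (i.e., number of knowledge questions correct among female and male participants". For all of them it specifies that "The models will include the cluster-level mean baseline outcome measure and stratification variables".

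Section 2.1 introduces this adjustment for female students present at endline, in the paragraph on the open cohort: "adjusting for cluster-level mean baseline measures of the relevant outcome where available". The boys are then treated separately: "Knowledge and attitudes among male students will be assessed through a closed cohort". Section 3.5 defines their endline analysis population in the sentence that begins "Outcomes among male students will be assessed in the closed cohort of male participants recruited at baseline who are enrolled at the same school at".

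On recruitment, Section 3.3 (Male students) says "Fifteen male S2 students per school were randomly selected to be recruited into a closed cohort at baseline" and "All male participants with baseline data were included in the cohort, even if enrolled after intervention activities started in the District". Section 5.1 lists male knowledge, myths and attitudes among the baseline characteristics to be described, so these scores were collected.

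Footnote 1 of Table A5, which serves the female and male rows alike, reads "Adjusted for baseline outcome measure, district, high/low school-level UNEB score, and school clustering". It does not say whether the baseline measure is the school's or the boy's.

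**The concern.** A school-mean covariate suits an open cohort, because girls who join late have no baseline outcome. The boys do not have that problem: having baseline data is how a boy enters the cohort. The plan carries the open-cohort device over to them without giving a reason.

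Three things are at stake for the male knowledge and attitude results:

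- Some precision may be given up.
- If the boys who leave differ between arms, a mean over everyone recruited does not describe the boys actually analysed. Section 5.3 does not say which of the two groups the male school mean covers.
- Girls count as baseline participants only if surveyed before activities began in their district (Section 3.3). Boys have no such limit. A late baseline score in an intervention school could already reflect exposure and would enter the covariate.

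**Working it through.** **The plan's own power figures.** Section 2.3 gives 84% power at 60 girls per school and 80% at 40, with 60 schools, ICC 0.05 and a difference of 0.2 SD. Effective number per arm = 30m / (1 + (m − 1) × 0.05).

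- m = 60: 1800 / 3.95 = 455.7. Noncentrality 0.2 × √(455.7/2) = 3.02. Power 85.5% (normal) or 84.3% (t, 58 df).
- m = 40: 1200 / 2.95 = 406.8. Noncentrality 2.85. Power 81.4% or 80.1%.

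Both figures reproduce. The SAP gives none for boys.

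**Inputs for boys.** From the SAP: 60 schools and m0 = 15 boys recruited per school. Assumed:

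- Retention of 82%, the pilot figure that Section 2.1 cites in the female context, so m1 = 15 × 0.82 = 12.3
- ICC ρ of 0.02 to 0.10
- Within-school correlation r between a boy's baseline and endline scores of 0.3 to 0.7
- School-level correlation R of 0.5 to 0.9

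**Formulas** (linear random-intercept model, total variance 1, equal school sizes, leaving at random):

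- Endline school mean: Vy = ρ + (1 − ρ)/m1
- Baseline mean of all recruited boys: Vx = ρ + (1 − ρ)/m0
- Their covariance: C = ρR + (1 − ρ)r/m0
- School mean only: A = Vy − C²/Vx
- Own score only: B = Vy − 2r[ρR + (1 − ρ)r/m1] + r²Vy
- Own score plus school mean: D = B − (C − rVx)²/Vx

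The arm effect is estimated between schools, so the standard-error ratio of school mean only to both is √(A/D).

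**Results at ρ = 0.05, r = 0.5**

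- 82% retention, R = 0.5: Vy = 0.1272, Vx = 0.1133, C = 0.0567. A = 0.0989, D = 0.0954. Ratio 1.018.
- 82% retention, R = 0.7: C = 0.0667, A = 0.0880, B = 0.0854, D = 0.0845. Ratio 1.020.
- Full retention, R = 0.7: A = 0.0741, B = 0.0750, D = 0.0741. Ratio 1.000.

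**Wider range at 82% retention.** The school-mean model has a standard error 0.4% to 6.7% larger than the model with both over the main set of combinations. The upper end becomes 7.5% if every pairing of R = 0.5, 0.7, 0.9 with r = 0.3, 0.5, 0.7 is allowed. If the school mean is taken over analysed boys only, the excess stays below 1%. Compared with the own score alone, the school mean ranges from 3.8% smaller to 6.7% larger, so the own score should be added to the school mean and not replace it.

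**Simulation check.** Counts of 0 to 9 were simulated for 60 schools of 15 boys and fitted by Poisson GEE, 400 replicates per setting. The empirical SD of the log rate ratio with the school mean only exceeded that with both by 0.8% at full retention (r = 0.5). At 82% retention the excess was 0.9%, 1.5% and 6.0% for r = 0.3, 0.5 and 0.7. Monte Carlo error comes on top.

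**Attrition.** Suppose selective leaving opens a baseline gap of d SD between the arms' analysed boys. A mean over all recruited boys does not register the gap, and about r × d carries into the endline comparison in a linear model: half the gap at r = 0.5. Adjusting for the boy's own score addresses this component.

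**The case against.** The strongest reply is that school-mean adjustment is valid and pre-specified, and that allocation was by school. The covariate is the observed mean of the same sampled boys, so their sampling deviations appear in both the baseline and the endline mean, and the covariate does remove within-school variance. With complete follow-up and equal school sizes, adding the individual score leaves the linear estimate unchanged. This stands, and it is why the precision argument is weak.

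A reader might assume the opposite, that a school mean leaves all within-school variance in place. At ρ = 0.05, r = 0.5 and R = 0.5 that would give √[(0.0375 + 0.0579)/(0.0375 + 0.0772)] = 0.91, a 9% reduction in standard error. The formula fits only a covariate unrelated to which boys were sampled, and Sections 3.3 and 3.5 describe the same boys at both surveys. The reduction is 1.8%.

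A reader might also take the Table A5 footnote as a rival, individual-level model for boys. The documents do not support that. The same footnote covers female rows for which Sections 5.2 and 5.3 specify the school mean, and its wording recurs under Tables A6 and A7. It is shorthand that omits the level.

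Finally, no differential attrition among boys is shown, and these are secondary outcomes that Section 6.2 says will be interpreted cautiously. That limits the weight of the point. It does not supply a reason to leave collected scores unused.

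**Conclusion.** The point holds as a minor one. Section 5.3 extends an open-cohort adjustment to a closed cohort and leaves the boys' own baseline scores out.

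The precision cost is nil with full follow-up in a balanced linear model, about 2% of the standard error at 82% retention with ICC 0.05 and r = 0.5, and roughly 0.4% to 7% over the wider assumptions. Whether the school mean covers recruited or analysed boys decides most of it.

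The better argument is protection against baseline differences created by boys leaving. How large those differences are cannot be judged from the SAP. Male ICC, correlations and retention are all assumed here. The primary outcomes and the female analyses are unaffected.

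**What to change.** - In Section 5.3, for the male knowledge and myths and attitudes outcomes, include each boy's own baseline score together with the school mean. Say whether that mean covers all recruited or only analysed boys.
- Keep the school-mean-only model as a sensitivity analysis.
- In Table A5, state the level of the baseline covariate: school mean for the female rows, own score plus school mean for the male rows.
- Form the male baseline covariate from scores taken before activities started in the district, and state in advance how boys surveyed later are handled.

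The cost is a few lines of SAP text and one added covariate from data already collected. The small downside is the extra rule for late-surveyed boys. The school-mean rule for the female open cohort stays as it is.
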